### Delays

Carboplatin should be administered, if possible, on the same day of each cycle with no more than 3 days deviation. From there, a delay will be defined as a period of more than 24 days between 2 subsequent infusions (from the second infusion). The number of days delay will be calculated as follows:

$$[\text{date of infusion (i)} - \text{date of infusion (i-1)}] - 24 \text{ days, where } i=2,3,..I$$

If the value above is >0 days, then this will be classed as a delay. A subject may have more than one treatment delay throughout the course of treatment.

The summary of carboplatin treatment exposure and compliance table will include the following information:

- Duration of carboplatin therapy (weeks): summary statistics.
- Number of initiated cycles for carboplatin: summary statistics
- Total number of carboplatin infusions received: number of subjects with infusions: 0, 1, 2, 3, 4, 5, 6, others, missing
- Cumulative actual treatment dose of carboplatin (mg): summary statistics.
- Dose intensity of carboplatin (mg/ 3 weeks) overall and by cycle: summary statistics.
- Relative dose intensity of carboplatin (%): < 60%, 60% - < 80%, 80% - < 90%, 90% - 110%, > 110%.

- Number of subjects with delayed carboplatin infusions, and maximum length of delay (no delay including 1-2 days delay, 3-8 days, 9-15 days,  $\geq 16$  days)

An additional table will provide the following statistics:

- Overall duration of cisplatin and carboplatin treatment (weeks) defined as:

$$\text{overall duration} = \left( \frac{(\text{date of last dose} - \text{date of first dose}) + 21}{7} \right)$$

where date of last dose is the latest date between last dose of cisplatin and last dose of carboplatin, and date of first dose is the first dosing date of cisplatin.

- Overall number of cycles from the date of first dose of cisplatin until the latest date between last dose of cisplatin and last dose of carboplatin
- Number of subjects with cisplatin treatment by cycle
- Number of subjects with carboplatin treatment by cycle

In addition, a listing will provide detail on carboplatin exposure for each subject based on “Carboplatin administration” eCRF page.

## 15.4 5-FU Exposure

Analysis of 5-FU exposure will be based on the calculated actual dose levels (total dose administered (mg) / BSA (body surface area in  $\text{m}^2$ )). For total dose administered, the actual dose administered as entered in the eCRF pages will be used. For BSA, BSA value collected on the “BSA Determination” eCRF page will be used. The last available BSA of the subject on or prior to the day of dosing will be used.

The number of initiated cycles for 5-FU:

A cycle is considered initiated if at least one non-null dose of 5-FU was administered during this cycle.

The duration of 5-FU treatment (in weeks) during the study is defined as:

$$\text{duration of 5-FU} = \left( \frac{(\text{stop date of last dose of 5-FU} - \text{start date of first dose of 5-FU}) + 16}{7} \right)$$

The total number of 5-FU infusions per subject is the count of the infusions with non-zero dose of 5-FU that the subject received.

The cumulative actual treatment dose ( $\text{mg}/\text{m}^2$ ) of 5-FU per subject is the sum of the calculated actual dose levels of 5-FU that the subject received.

The dose intensity (mg/m^2/3 weeks) of 5-FU and the relative dose intensity (%) of 5-FU will be calculated for a 3-weekly cycle:

$$\text{dose intensity of 5-FU} = \left( \frac{\text{Cumulative dose of 5-FU from 1st infusion}}{\text{duration of 5-FU in weeks} / 3} \right)$$

The relative dose intensity (%) of 5-FU is defined as the dose intensity of 5-FU divided by 750\*5 mg/m^2/3 weeks (the planned dose per cycle for 5-FU as assigned in the protocol).

The summary of 5-FU treatment exposure and compliance table will include the following information:

- Duration of 5-FU therapy (weeks): summary statistics.
- Number of initiated cycles for 5-FU: summary statistics
- Total number of 5-FU infusions received: number of subjects with infusions: 0, 1, 2, 3, 4, 5, 6, others, missing
- Cumulative actual treatment dose of 5-FU (mg/m^2): summary statistics.
- Dose intensity of 5-FU (mg/m^2/3 weeks) overall and by cycle: summary statistics.
- Relative dose intensity of 5-FU (%): < 60%, 60% - < 80%, 80% - < 90%, 90% - 110%, > 110%.
- Number of subjects per minimum relative dose category (as defined Section 15.1)
- Number of subjects with delayed 5-FU infusions, and maximum length of delay (no delay including 1-2 days delay, 3-8 days, 9-15 days, ≥16 days)

In addition, a listing will provide detail on 5-FU exposure for each subject based on “5-FU administration” eCRF page.

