6.4.1.1 Selection and Timing of Chemotherapy

6.4.1.1.1 Cisplatin

Cisplatin (75 mg/m²) will be administered as intravenous infusion (refer to China package insert) on Day 1 of each 21-day treatment cycle.

For any BSA value more than 2.0 m², the cisplatin dosage must be restricted to the dose appropriate for a BSA of 2.0 m². Adequate hydration and maintenance of sufficient urinary output is mandatory. Centers should follow their related local practice and the approved local package insert or the following hydration scheme:

- Before cisplatin: 2 liters of any fluid taken orally on the day before chemotherapy AND 1 liters orally plus a minimum of 500 mL of intravenous fluid given on the morning of cisplatin treatment. The 500 mL of intravenous fluid may be part of the antiemesis infusion.
- After cisplatin: Immediately after cisplatin, an intravenous infusion of 200 to 250 mL/hour of 5% dextrose in half normal saline, 5% dextrose in normal saline, or normal saline and 30 mEq KCl/L will be given for 4 to 6 hours.

Total hydration fluid volume, including enteral and parenteral, should be at least 3500 mL on the day of cisplatin administration.

There must be at least 1 hour between the end of the cetuximab infusion and the start of the cisplatin infusion. Intravenous prehydration can be performed concomitant to cetuximab administration but a separate line must be used.

Document No. CCI
Object No.

¹ If cisplatin results in a nonhematologic toxicity (see Section 6.4.1.2.2), cisplatin may be replaced by carboplatin in subsequent cycles.

Antiemetic prophylaxis is mandatory to prevent acute and delayed nausea and vomiting due to the high emetogenicity of cisplatin. It is highly recommended that the guidelines of the Multinational Association of Supportive Care in Cancer and the American Society of Clinical Oncology are followed, i.e., inclusion of dexamethasone, a 5-hydroxytryptamine-3 antagonist and a neurokinin-1 antagonist.

All infusions and medications given for hydration, urinary output maintenance and antiemesis must be documented in the eCRF. Investigators should refer to the approved cisplatin package insert for additional information such as safety issues, adverse reactions, and storage information.

Exact documentation of the actual doses, dates, and start and end times of infusions is mandatory.

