6.4.1.1.2 Carboplatin

If cisplatin results in a nonhematologic toxicity (see Section 6.4.1.2.2), carboplatin at a dose of target AUC=5 may be used as the replacement of cisplatin in subsequent cycles. The decision needs to be made in discussion with the Medical Monitor on a case-by-case basis.

Carboplatin will be administered using an intravenous infusion of 15 minutes or longer (refer to China package insert) on Day 1 of each 21-day treatment cycle. The dose of carboplatin will be calculated considering the subject's renal function as described by the glomerular filtration rate using the Calvert formula or the Chatelut formula, given that the target AUC is 5.

For those subjects in Arm A, there must be at least 1 hour between the end of the cetuximab infusion and the start of the carboplatin infusion.

Exact documentation of the actual doses, dates, and start and end times of infusions is mandatory.

6.4.1.1.3 5-Fluorouracil

Investigators should treat subjects with commercially available forms of 5-FU, and must refer to the approved 5-FU prescribing information on dosage and administration, safety issues (warnings, precautions), adverse reactions, dose reductions and omissions. Investigators should also follow their related local practice for the administration of 5-FU.

5-Fluorouracil will be administered as a dose of 750 mg/m²/day as a continuous intravenous infusion over 24 hours a day from Day 1 to Day 5 (± 6 hours of the overall duration) of each 21-day treatment cycle. Administration of 5-FU is to start upon completion of cisplatin/carboplatin administration and may be performed via the same infusion line.

For those subjects in Arm A, there must be at least 1 hour between the end of the cetuximab infusion and the start of the 5-FU infusion.

Exact documentation of the actual doses, dates, and start and end times of infusions is mandatory.

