6.9 Assessment of Investigational Medicinal Product Compliance

Cetuximab treatment and chemotherapy will be administered either by the Investigator or under his or her supervision in an inpatient setting.

The application dates and exact amounts of cetuximab, cisplatin, carboplatin, and 5-FU given at each infusion will be documented in the eCRF. If cetuximab and/or cisplatin and/or carboplatin and/or 5-FU treatment is interrupted during the actual infusion, the clinical staff will estimate the percentage of the dose received by the subject and document it in the eCRF.

Any reason for noncompliance should also be documented. Insufficient compliance is defined as a subject missing > 2 consecutive infusions of cetuximab or > 21 consecutive days chemotherapy infusion delay for nonmedical reasons. In the event of insufficient compliance, discontinuation of the trial treatment will be considered in mutual agreement between the Investigator and Sponsor on a case-by-case basis.

The IMP administration must be recorded in the eCRF.

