8.5.4 Analysis of Safety

Safety analyses will be performed according to the as-treated principle. Any TEAEs will be summarized, i.e., those events that emerge during treatment having been absent pre-treatment, or worsen relative to the pre-treatment state and with onset dates occurring within the first dosing day of trial treatment until 30 days after the last dose of trial treatment. No formal statistical comparisons are planned.

The extent of exposure for cetuximab, cisplatin or carboplatin, and 5-FU will be characterized by duration (weeks), cumulative dose, dose intensity, relative dose intensity (actual dose given/planned dose), number of dose reductions, and number of dose delays.

AEs will be coded according to the current Medical Dictionary for Regulatory Affairs (MedDRA). The severity of AEs will be graded using CTCAE toxicity grades. The incidence and type of AEs, SAEs, trial treatment-related AEs and SAEs, trial treatment-related AEs by CTCAE toxicity grade, CTCAE Grade 3 and 4 AEs, trial treatment-related CTCAE Grade 3 and 4 AEs, AEs leading to death, AEs leading to discontinuation of trial treatment, will be summarized in total and for each treatment arm according to the MedDRA system organ class and MedDRA preferred terms. Missing classifications concerning trial treatment relationship will be considered as related to the trial treatment.

All deaths, deaths within 60 days after date of first dose of trial treatment and deaths within 30 days after last dose of trial treatment as well as reasons for deaths will be tabulated.

Laboratory results will be classified according to the CTCAE (version 4.03) when applicable. The worst on trial grade after date of first dose of trial treatment will be summarized. Shifts in toxicity grading from treatment start to highest grade will be displayed. Results for variables that were not part of the CTCAE (version 4.03) will be presented as below, within, and above the normal limits of the local laboratory. Only subjects with post-baseline laboratory values will be included in these analyses. The last measurement before trial treatment will serve as the baseline measurement.

Vital signs (temperature, heart rate, blood pressure, respiratory rate) will be descriptively presented.

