## 15.2 Cisplatin Exposure

Analysis of cisplatin exposure will be based on the calculated actual dose levels (total dose administered (mg) / BSA (body surface area in m^2). For total dose administered, the actual dose administered as entered in the eCRF pages will be used. For BSA, BSA value collected on the

“BSA Determination” eCRF page will be used. The last available BSA of the subject on or prior to the day of dosing will be used.

The number of initiated cycles for cisplatin:

A cycle is considered initiated if at least one non-null dose of cisplatin was administered during this cycle.

The duration of cisplatin treatment (in weeks) during the study is defined as:

$$\text{duration of cisplatin} = \left( \frac{(\text{date of last dose of cisplatin} - \text{date of first dose of cisplatin}) + 21}{7} \right)$$

The total number of cisplatin infusions per subject is the count of the infusions with non-zero dose of cisplatin that the subject received.

The cumulative actual treatment dose (mg/m^2) of cisplatin per subject is the sum of the calculated actual dose levels of cisplatin that the subject received.

The dose intensity (mg/m^2/3 weeks) of cisplatin and the relative dose intensity (%) of cisplatin will be calculated for a 3-weekly cycle:

$$\text{dose intensity of cisplatin} = \left( \frac{\text{Cumulative dose of cisplatin from 1st infusion}}{\text{duration of cisplatin in weeks} / 3} \right)$$

The relative dose intensity (%) of cisplatin is defined as the dose intensity of cisplatin divided by 75 mg/m^2/3 weeks (the planned dose per cycle for cisplatin as assigned in the protocol).

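### Two SAP exposure formulas slightly misstate chemotherapy dose intensity: 5-FU when the last infusion is cut short, and cisplatin when the protocol's BSA cap applies

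*SAP*

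**What the plan says.** **5-FU.** SAP 15.4 defines duration in weeks as the interval from the start date of the first dose to the "stop date of last dose of 5-FU", plus 16 days, divided by 7. Dose intensity is the cumulative dose over that duration, per 3 weeks. RDI divides dose intensity by 750 × 5 = 3750 mg/m² per 3 weeks, described as "the planned dose per cycle for 5-FU as assigned in the protocol". RDI is tabulated in five categories: below 60%, 60 to below 80%, 80 to below 90%, 90 to 110%, and above 110%. Dose intensity itself is reported as summary statistics. Protocol 6.4.1.1.3 schedules the infusion "from Day 1 to Day 5 (± 6 hours of the overall duration) of each 21-day treatment cycle". Protocol 6.9 foresees partial infusions: where one "is interrupted during the actual infusion, the clinical staff will estimate the percentage of the dose received by the subject", the estimate goes into the eCRF.

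**Cisplatin.** SAP 15.2 takes the mg given, divides by the last value on the BSA Determination eCRF page, and continues: "The relative dose intensity (%) of cisplatin is defined as the dose intensity of cisplatin divided by 75" mg/m² per 3 weeks. The minimum relative dose table in SAP 15.1 uses the same scale, with 67.5 mg/m² as the 90% line. Protocol 6.4.1.1.1 says that above 2.0 m² "the cisplatin dosage must be restricted to the dose appropriate for a BSA of 2.0" m². Protocol 8.5.4 defines "relative dose intensity (actual dose given/planned dose").

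**Comparators in the SAP.** Cisplatin and carboplatin durations (15.2, 15.3) run to the date of the last dose plus 21 days. Carboplatin RDI is already measured against the subject's own planned dose. SAP section 9 declares no change from the protocol's planned analyses.

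**The concern.** An exposure formula should return 100% for a subject who received exactly what the protocol planned, and should show the whole shortfall for one who did not. Each rule misses one of these for a record that the protocol anticipates.

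For 5-FU, the constant 16 completes a 21-day cycle only when the last infusion spans 5 calendar days. If that infusion is stopped early, the undelivered days leave both the numerator and the denominator, so part of the shortfall cancels. An infusion at which 5-FU is stopped for good is by definition the last one, which is where the formula is sensitive. For cisplatin, a subject above 2.0 m² who receives the full protocol dose is scored below 100%.

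At stake is the accuracy of the descriptive account of chemotherapy delivery.

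**Working it through.** **5-FU inputs.** From SAP 15.4: 3750 mg/m² per cycle, 750 mg/m² per day, stop date plus 16. Let c be the number of cycles and d the days of the last infusion that were delivered. Earlier cycles are taken as full dose and on time. A full 120-hour infusion started on Day 1 ends on Day 6, so stop minus start is 5.

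- Cumulative dose = 3750(c − 1) + 750d
- SAP days = 21(c − 1) + d + 16
- SAP RDI = cumulative dose / (SAP days / 21) / 3750
- RDI with a 21-day last cycle = cumulative dose / c / 3750

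Calibration: with d = 5 the SAP days are 21c and RDI is 100.0% for 1 to 6 cycles, as intended.

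Last infusion cut short:

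| c | d | SAP days | SAP RDI % | 21-day RDI % | Excess (points) |
|---|---|---|---|---|---|
| 1 | 1 | 17 | 24.7 | 20.0 | 4.7 |
| 1 | 2 | 18 | 46.7 | 40.0 | 6.7 |
| 1 | 3 | 19 | 66.3 | 60.0 | 6.3 |
| 1 | 4 | 20 | 84.0 | 80.0 | 4.0 |
| 5 | 2 | 102 | 90.6 | 88.0 | 2.6 |
| 6 | 1 | 122 | 89.5 | 86.7 | 2.8 |
| 6 | 2 | 123 | 92.2 | 90.0 | 2.2 |
| 6 | 3 | 124 | 94.8 | 93.3 | 1.5 |
| 6 | 4 | 125 | 97.4 | 96.7 | 0.8 |

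Example, c = 1 and d = 2: 1500 / (18/21) / 3750 = 46.7%, against 1500/3750 = 40.0%.

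Of the 24 combinations (c = 1 to 6, d = 1 to 4), one changes RDI category: c = 5, d = 2, which moves from 80 to below 90% into 90 to 110%. With every dose at the 80% level, two of the 24 change; for example, c = 2, d = 2 gives 60.3% against 56.0%.

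Stop-date convention: if sites date a complete infusion Day 1 to Day 5, stop minus start is 4. One complete cycle then gives 21/20 = 105.0%, and six give 126/125 = 100.8%. For truncated infusions the excess becomes 6.3 to 10.0 points for one cycle and 1.6 to 3.6 for six, and three of the 24 full-dose combinations change category. The SAP does not say which convention applies.

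**Cisplatin inputs.** Cap at 2.0 m² (Protocol 6.4.1.1.1), so the full dose above it is 75 × 2.0 = 150 mg; reference 75 mg/m² (SAP 15.2); 90% line 67.5 mg/m² (SAP 15.1).

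Calibration: an uncapped, on-time full course gives 100.0%.

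Capped subject at full dose: dose level = 150/BSA; RDI = (150/BSA)/75 = 200/BSA %.

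| BSA (m²) | mg/m² | SAP RDI % | Actual/planned % |
|---|---|---|---|
| 2.1 | 71.4 | 95.2 | 100 |
| 2.2 | 68.2 | 90.9 | 100 |
| 2.25 | 66.7 | 88.9 | 100 |
| 2.4 | 62.5 | 83.3 | 100 |

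The 90% line is crossed at 150/67.5 = 2.22 m². By the Mosteller formula at 180 cm, 2.0 m² is 80 kg and 2.22 m² is about 99 kg.

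The documents give no BSA distribution. Assuming a normal distribution with mean 1.65 to 1.75 and SD 0.15 to 0.17, about 1 to 7% of 240 subjects (2 to 17) exceed 2.0 m², and fewer than one is expected above 2.22 m².

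**The case against.** The strongest reply is that almost nothing a reader looks at will move. 5-FU RDI is shown only in categories, and the largest excesses belong to one-cycle subjects, who stay in the same category. Cumulative 5-FU dose has no duration in it. Dose intensity by cycle will show a truncated infusion in full if the fixed cycle windows of SAP 15.2 are also used for 5-FU. Capped cisplatin subjects stay in the 90 to 110% RDI row and the 90%-or-above minimum-dose row up to 2.22 m². The 100% row of the minimum-dose table is best read as the reference line, since the rows below it already cover every value. All of this stands and limits the point to a minor one.

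It is also fair that the BSA page is not stated to hold uncapped BSA. That remains an inference, though a strong one: the same page serves cetuximab and 5-FU, for which the protocol states no cap.

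The reply does not remove the error. The dose-intensity summaries do carry the 5-FU excess and the cisplatin shortfall, and nothing else in the SAP corrects either formula.

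A reader might go further and infer that these are ordinary records, that capped subjects will be presented as under-dosed, or that the comparison of chemotherapy delivery between arms is distorted. The documents do not support this. They give no rate of truncated last infusions and no BSA distribution, and the cap applies equally in both arms. Protocol 3.7.4 reports more cardiac ischemia with cetuximab plus infusional 5-FU, so early stops could be more frequent in Arm A, but no rate is given. Nor does the SAP say that RDI is meant to show whether cetuximab costs chemotherapy dose.

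**Conclusion.** Both formulas give slightly wrong values for records that the protocol foresees.

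- **5-FU:** RDI is overstated by 4.0 to 6.7 points for one cycle and 0.8 to 2.8 for six when the last infusion is stopped after 1 to 4 days. This assumes full earlier doses, no delays and a Day 6 stop date for a complete infusion. Categories seldom change. A complete single cycle dated Day 1 to Day 5 reads 105%.
- **Cisplatin:** a fully dosed capped subject reads 200/BSA % instead of 100%, provided that the BSA page is uncapped. The 90% line is crossed only above 2.22 m². The number of such subjects is not in the documents and is probably small.

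Only descriptive exposure summaries are affected. Protocol 8.5.4 plans no formal safety comparisons, and neither the PFS analysis nor any decision uses these values. The point is worth correcting because correction is cheap, not because conclusions depend on it.

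**What to change.** **SAP 15.4:** define 5-FU duration as (start date of last 5-FU infusion − start date of first 5-FU infusion + 21) / 7, matching cisplatin and carboplatin. This also removes the dependence on how the stop date is recorded.

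**SAP 15.2 and the minimum-dose table in 15.1:** for cisplatin RDI and the minimum relative dose category, use the protocol-planned dose, 75 mg/m² × min(BSA, 2.0 m²), as the reference. Leave the reported actual mg/m² and cumulative dose on actual BSA, so that they still describe dose per body surface. State that the BSA page holds the uncapped value.

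The cost is a few formula edits and a table footnote, with data already collected and no change to any dosing rule. 5-FU RDI becomes slightly lower for subjects whose last infusion was cut short. For capped subjects, cisplatin RDI will no longer equal the tabulated dose intensity divided by 75, which the footnote should explain.

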## 16 Endpoint Evaluation

The ITT analysis set will be used for endpoint evaluation. Efficacy analysis will be repeated on the PP analysis set only if the PP set represents less than 90% of the ITT analysis set.

### 16.1 Primary Endpoint Analyses

#### 16.1.1 Primary Analysis of Progression Free Survival (PFS)

Analysis Set

- ITT, PP (as sensitivity analysis if less than 90% of ITT)

The primary endpoint of this trial is PFS time as assessed by independent radiology read. IRC will perform *radiology* and *clinical* reviews as described in the IRC Charter. The results of the *radiology* review will be used for the primary analysis.

The PFS time by IRC is defined as the duration (in months) from the date of randomization until first observation of PD (based on imaging as assessed by IRC), or death due to any cause when death occurs within 60 days after the last tumor assessment or the randomization (whichever is later).

Any subject with neither assessment of tumor progression, nor death date within 60 days after last tumor assessment or randomization will be censored on the date of last tumor assessment or randomization. A subject who has not received trial treatment and for whom no date of progression or death is known will be censored on the date of randomization (Day 1) or date of last tumor assessment, whichever comes later. The following censoring rules will be applied.

